## 7 General Considerations

Analysis datasets will be created according to CDISC standards and the Study Data Standardization Plan, and data will be displayed according to reporting standards in this SAP.

SAS version 9.3 or higher will be used to perform all data analyses and to generate tables, figures, and listings.

Continuous variables will be summarized in terms of the number of observations, mean, standard deviation, median, Q1, Q3, minimum, and maximum. Other descriptive statistics (eg, coefficient of variation, geometric mean) may be reported when appropriate. Categorical variables will be summarized using frequency counts and percentages. Analyses that use other descriptive statistics will have the specific descriptive statistics required identified with the analysis in the applicable SAP section.

All listings will include subject number, treatment sequence, and randomized treatment of the respective treatment sequence. Unless otherwise stated, all listings will be sorted by treatment sequence, subject number, and then by numeric visit date and time. If any of these variables do not apply to a listing, then that listing will use only those that do in the order given here.

Summary statistics of central tendency will be reported to one more decimal place than the collected data. Summary statistics of variability will be reported to one more decimal place than the commensurate measure of central tendency. For example, the mean and median for age will be reported to one decimal place because it is collected in full years. The standard deviation of age will then be reported to 2 decimal places. Percentages will be displayed to one decimal place.

P-values will be presented with 6 decimal places for primary and key secondary endpoints to ensure proper comparison to significance levels.

Formatting for dates and times will be:

- Dates only – ddmmmyyyy
- Times only – hh:mm or hh:mm:ss (as appropriate)
- Dates and times – ddmmmyyyy hh:mm or ddmmmyyyy hh:mm:ss (as appropriate)

Generally, only pre-specified planned times will be used in the summaries, statistical analyses, and calculations of any derived parameters; unscheduled readings will be included in the listings.

Actual, rather than planned, sampling times will be used in the derivation of PK parameters and in the individual concentration-time plots and listing of PK concentration data. Planned times will be used in the descriptive summaries and in mean plots. Concentration-time data will be listed according to actual sampling times relative to dosing time.

Assessment windows will not be defined for the purpose of classifying measurements obtained outside scheduled assessment times.

Deviations from the analyses in this SAP will be identified in the CSR.

## 7.1 Multicenter Studies

Pooling of centers will be done for subgroup analysis (see Section 10.2.2). No other pooling of centers will be done.

## 7.2 Treatment and Visit Descriptors

Period descriptions will show the weeks of interest, eg, Study Period 1 (Week 1 to 25), Study Period 2 (Week 25 to 53) or Study Period 3 (Week 53 to EOP3).

---

Sequence descriptions will display the respective treatment or treatment sequence.

The line displayed for visit “Baseline” comprises all baseline assessments as defined in Section [8.2.5](#), which is not necessarily identical to the summary of all assessments from the visit Baseline.

According to the protocol, for subjects who discontinue IMP early during participation in Study Period 1 or Study Period 2, all Week 53 assessments will be performed at the study visit where IMP treatment is discontinued instead of the assessments scheduled for that particular study visit. The Week 53 assessments will be assigned as follows:

- For subjects who discontinue IMP early in Study Period 1 -> EOT P1
- For subjects who discontinue IMP early in Study Period 2 -> EOT P2
- For subjects who do not discontinue IMP early in Study Period 1 or 2 -> Week 53

Analyses by visit will include for the EOT P1 visit the last assessment in Study Period 1 and for EOT P2 the last assessment in Study Period 2.

### 7.3 Multiple Comparisons and Multiplicity

Issues related to multiplicity are described in Section [4.2.2](#).

### 7.4 COVID-19 Impact

During the course of this study, the global COVID-19 pandemic occurred, impacting the study in a variety of ways. This section describes how the impact of COVID-19 will be reported.

#### Subject Disposition: Study Treatment Discontinuation or Study Discontinuation

Subjects who experience either study treatment discontinuation or study discontinuation due to COVID-19 will have the reason captured in the eCRF. On the appropriate eCRF form to record either study medication discontinuation (“End of Treatment” and / or “End of Treatment Period 3” form) or study discontinuation (“Conclusion of Subject Participation” form), a reason will be selected which includes a field for descriptive text. The reason can be either “Withdrawal by Subject,” “Physician Decision,” or “Other”. The associated free text field entry will include “COVID-19”. When either treatment or the study is discontinued due to an AE or death, the

specific corresponding AE is collected. Discontinuations due to COVID-19 adverse events will then be identified based on whether the MedDRA code for the AE is included in the broad COVID-19 standard MedDRA query (SMQ).

Cases of study treatment discontinuation or study discontinuation due to COVID-19 will be included in the summary of subject disposition.

#### Demographic and Baseline Characteristics

As only 2 subjects have been enrolled and randomized prior to the COVID-19 pandemic onset, demographic and baseline characteristics will not be summarized by COVID-19 period, ie before and after pandemic onset. COVID-19 pandemic onset will be considered to be 1-Feb-2020.

Subjects with enrollment date after the pandemic onset will be flagged in the listings of demographic and baseline characteristics.

#### Adverse Events

Adverse events associated with COVID-19, which can include a clinically significant laboratory finding like a positive test result for COVID-19, will be reported by investigators following reporting requirements outlined in the protocol. COVID-19 associated adverse events are identified via MedDRA coding. Relevant adverse events will be identified for reporting by the broad COVID-19 standard MedDRA query (SMQ). All COVID-19 associated adverse events will be included in standard AE tables.

An overview summary table of COVID-19 associated treatment-emergent adverse events (TEAEs), including number and percentages of subjects as well as the number of events, will be provided for the following:

- Any TEAE
- Serious TEAE
- TEAE resulting in death
- TEAE leading to discontinuation of study treatment
- TEAE leading to dose interruptions
- TEAE leading to study withdrawal
- TEAE by maximum severity (mild, moderate, severe, missing)

A listing showing all COVID-19 associated adverse events will be provided.

---

### COVID-19 Vaccinations

Sites will be prompted to inquire whether a subject has received a COVID-19 vaccination and to record each dose of the vaccine on the concomitant medications form along with the exact date of administration and manufacturer of the vaccine. Standardised Drug Grouping (SDG) from WHO Drug Dictionary will be utilized to identify COVID-19 vaccines using the narrow SDG ‘Vaccines for COVID-19’. Any vaccination related adverse events experienced by study participants will be recorded on the AE/SAE eCRF page. As a mechanism to assess potential TEAEs associated with the COVID-19 vaccines, those TEAEs occurring within 7 days after COVID-19 vaccine administration will be summarized.

The data will be summarized as described below:

- Summary table by SoC and PT of all TEAEs occurring within 7 days after COVID-19 vaccine administration
- All TEAEs except those occurring within 7 days of COVID-19 vaccination

In addition, the following listings will be provided:

- Listing of all AEs occurring within 7 days after COVID-19 vaccine administration
- Listing of all subjects receiving COVID-19 vaccine

### Visit Modality, Missed Visits and Missing Assessments

Changes to subjects’ visits caused by the COVID-19 pandemic will be captured for each subject in the eCRF, on the “Visit Status” form. The eCRF page includes different options for the primary visit modality, as well as whether the missed visit/alternate visit modality is due to COVID-19. Since assessments (eg vital signs, laboratory data) collected at each visit are known, the data missing due to COVID-19 can be determined.

Assessments that were missed or required alternate visit modality (eg, televisits or home health visits) due to COVID-19 will be summarized. In addition, number of subjects with missed visits or alternate visit modality, by visit, will be summarized. Data will be listed.

### Protocol Deviations

Protocol deviations due to the COVID-19 pandemic will be collected in the Clinical Trial Management System (CTMS) per the study specific Protocol Deviation plan. Pandemic related protocol deviations are identified within CTMS using the sub-category ‘COVID-19 Restrictions’.

COVID-19-related protocol deviations will be summarized as sub-categories under existing categories of protocol deviations (see Section 9.2). All COVID-19 related protocol deviations will appear in the listing of protocol deviations and will be flagged.

### Overview of COVID-19 Impact

Number and percentages of subjects with at least one of the following due to COVID-19 will be summarized in an overview table:

- Subjects with Any COVID-19 Impact
- Protocol Deviations
- Missing assessment
- Missing Visit
- Alternate Visit Modality
- Study Treatment Discontinuation
- Study Discontinuation
- Any TEAEs
- Any Serious TEAEs

## 8 Data Handling Conventions

### 8.1 Missing Data

#### 8.1.1 Imputation of Non-Date Missing Data

Per the protocol, subjects will be encouraged to remain in the study for the remainder of the phase during which they discontinue IMP, in order to collect further study assessments. Missing efficacy data will occur if a subject withdraws consent for additional post-discontinuation assessments. Below is how the missing efficacy data are handled in the key efficacy analyses:

- The primary endpoint analysis considers subjects discontinuing from the study before Week 25 as Non-responders, except for subject who discontinue due to the Ukraine war (see Section 10.2). This consideration is modified in the sensitivity analyses detailed in Section 10.2.1.
- The three continuous key secondary efficacy endpoints are analyzed with MMRM under the Missing at Random (MAR) assumption. No missing data imputation is required for this analysis approach.
- Tipping point analyses will be performed for the key secondary endpoint analyses.

The handling of missing data from questionnaires, CSMs, and other data collection instruments is described in the respective section of the specific instrument.

Subjects with the designation of relationship to IMP and/ or oral corticosteroid treatment for adverse events (AEs) and serious adverse events (SAEs) missing will have the worst case assumed to impute the relationship to IMP:

Relationship as entered in eCRF		Imputed relationship *	
to IMP	to oral corticosteroid treatment	to IMP	to oral corticosteroid treatment
missing	missing	related	not related
related	missing	related	not related
not related	missing	not related	related **
missing	related	not related	related
missing	not related	related	not related

\* Italic font is used for imputed values

\*\* Only if start of oral corticosteroid treatment was before or at start of AE, otherwise *not related*

There will be no other imputation for missing data other than as described in Section 8.1.2 for partial dates and times.

If the study is terminated early, all available data will be listed, and a review carried out by the study team to assess which statistical analyses are to be performed.

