### 9.3 Causality of Adverse Events

The causal relationship of an AE to either IMP or corticosteroid treatment **must always be assessed** by the investigator (Treating Physician). All AEs will be classified as either **related** or **not related** to either IMP or corticosteroid treatment. The AE eCRF will provide the

option to select either IMP or corticosteroid treatment relatedness (see [Section 8.1.2.1](#) for Monitoring for Corticosteroid Treatment).

Adverse events attributable to corticosteroid administration include but are not limited to the following [[Oray et al, 2016](#)]:

- Uncontrolled hypertension defined as average systolic blood pressure  $\geq 140$  mmHg and/or average diastolic blood pressure  $\geq 90$  mmHg
- Hypokalemia
- Hyperglycemia
- Weight gain  $\geq 5\%$ , increase in waist circumference
- Osteopenia or osteoporosis
- Depression, mania, or other relevant psychiatric diagnoses
- Evidence of peptic ulcer disease or erosive gastritis

The degree of certainty with which an AE is attributed to IMP or an alternative cause (eg, corticosteroid treatment, natural history of the underlying disease, other concomitant therapy) will be determined by how well the event can be understood in terms of:

- Known pharmacology of IMP
- Clinically and/or pathophysiologically plausible context
- Reaction of a similar nature previously observed with similar products, or reported in the literature for similar products as being product related (eg, headache, facial flushing, pallor)
- Plausibility supported by the temporal relationship (eg, the event being related by time to administration or termination of treatment with IMP or corticosteroid treatment, drug withdrawal or reproduced on rechallenge)

When there is uncertainty whether an AE is related to IMP or corticosteroid treatment, the AE should be considered related to IMP. If a causality assessment is not provided for an AE (including an SAE), that AE will be considered related to IMP.

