Secondary Safety		
2,3,4	Treatment-emergent adverse events (TEAEs)	
 
Percentage of subjects with TEAEs
 
Percentage of subjects with related TEAEs
 
Percentage of subjects with serious TEAEs
 
Rate of TEAEs per time at risk
 
Rate of mild, moderate, and severe TEAEs per time at risk
 
Rate of related TEAEs per time at risk
 
Rate of serious TEAEs per time at risk
 

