### **5 Changes in the Conduct of Planned Analyses**

There were no changes to analyses planned in the study protocol.

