## 11.2 Adverse Events

Adverse events will be coded using the Medical Dictionary for Regulatory Activities (MedDRA) version 21.0 or higher. TEAEs are defined as AEs started after the start of the first infusion of IMP. All AEs regardless of when they were reported will be listed.

In addition to an overall TEAE analysis, the analysis will be repeated for each period. An AE will be counted in the respective analysis, if the onset of the event falls within the period. For the definition of start and end of the periods see [Table 8](#) and [Table 9](#).

- An overview summary of TEAEs, including number of subjects, percentages of subjects, the number of events, and TEAE rate per time at risk, including the following. This summary will also be provided for the subgroup of Japanese subjects and by age group (<65 year, ≥65 years):
  - Any TEAE
  - TEAEs related to IMP
  - TEAEs related to corticosteroid treatment

- Temporally associated TEAEs (defined as an AE with an onset between the start of the IMP infusion and up to 72 hours after the end of IMP infusion)
  - Related TEAEs or temporally associated TEAEs to IMP
  - TEAEs leading to permanent discontinuation of IMP
  - TEAEs leading to withdrawal from study
  - TEAEs leading to IMP dose interruptions
  - AESIs
  - AESIs related to IMP
  - Temporally associated AESIs (defined as an AESI with an onset between the start of the IMP infusion and up to 72 hours after the end of IMP infusion)
  - Serious TEAEs
  - Serious TEAEs related to the IMP
  - Serious TEAEs related to corticosteroid treatment
  - Temporally associated serious TEAEs
  - Fatal serious TEAEs
- 
- The following descriptive tables will be generated for TEAEs, including number of subjects, percentages of subjects, the number of events, and TEAE rate per time at risk. Analyses marked with \* will also be provided for the subgroup of Japanese subjects:
    - TEAEs by System Organ Class (SOC) and Preferred Term (PT)  
Note: This table will also be provided by age group (<65 year,  $\geq$ 65 years)
    - TEAEs by SOC, PT, and maximum severity\*
    - Causally related TEAEs by SOC and PT\*
    - Temporally associated TEAEs by SOC and PT\*
    - Causally related TEAEs or temporally associated TEAEs by SOC and PT
  

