  - All AE summaries presented by SOC and preferred term will include a virtual SOC comprising of local reactions, ie, all AEs reported within the MedDRA High level terms “Administration site reactions NEC” or “Infusion site reactions” or “Injection site reactions”. Local reactions will be analyzed by using a virtual SOC called “local adverse events”.

- All AE summaries presented by SOC and preferred term will include a virtual SOC “Thromboembolic Events” comprising all AEs reported within the MedDRA SMQs in Section 11.3.

All tables will be displayed in descending order of total incidence by preferred term and by SOC and PT, respectively.

TEAE rates per time at risk will be calculated as annualized TEAE rates using:

$$\text{Annualized TEAE rate} = \frac{\text{number of events}}{(\text{Total observational time in this period (days)} / 365.25)}$$

Number of events and total observational time are counted within the respective period and treatment group. Start dates and end dates to derive the observational time for the respective periods are defined in [Table 8](#) and [Table 9](#).

Temporally associated TEAEs are defined as AEs with an onset between the start of the infusion and up to 72 h after the end of IMP infusion. In case time of onset of AE is missing, the AE is considered temporally related, if the onset of the AE is between the day of the start of infusion and the day of the end of infusion + 3 days (inclusive).

The following listings will be provided:

- All Adverse Events
- All serious TEAEs

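### SAP 8.1.1 promises the worst case for a missing IMP causality, but one row of its table imputes the best case

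*SAP*

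**What the plan says.** SAP Section 8.1.1 covers adverse events for which the relationship to IMP, to oral corticosteroid, or to both is missing. Its rule in words is that such events "will have the worst case assumed to impute the relationship to IMP". A five-row table then gives the imputed pair of values for each pattern of missing entries. In the fourth row (IMP missing, corticosteroid *related*) the imputed IMP value is *not related*.

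Protocol 9.3 sets two default rules. For an absent assessment: "If a causality assessment is not provided for an AE (including an SAE), that AE will be considered related to IMP". For doubt between the two causes: "When there is uncertainty whether an AE is related to IMP or corticosteroid treatment, the AE should be considered related to IMP". The same section also says that the eCRF offers the "option to select either IMP or corticosteroid treatment relatedness".

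SAP Section 5 states: "There were no changes to analyses planned in the study protocol".

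The imputed variable feeds the safety results. SAP Table 1 lists the percentage of subjects with related TEAEs and the "Rate of related TEAEs per time at risk" among the secondary safety measures. SAP 11.2 summarizes IMP-related TEAEs, IMP-related AESIs and "Serious TEAEs related to the IMP".

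**The concern.** A programmer cannot follow both the sentence and the table. The sentence sends every missing IMP causality to *related*. The table sends one pattern to *not related*.

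The pattern is a plausible one. All subjects may be on background oral steroids, some receive rescue steroids, and an investigator who ticks steroid-related may leave the IMP field blank. If the table is followed, each such event is removed from the IMP-related event count, from the IMP-related rate and, in some cases, from the count of subjects with an IMP-related event. The product's related-event profile would then look slightly better than the SAP's declared convention allows. If the row is a departure from Protocol 9.3, it is also undisclosed, because Section 5 of the SAP reports none.

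**Working it through.** **Row check.** The stated rule is applied as follows: a missing IMP causality becomes *related*, and an entered IMP causality is kept.

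| Row | IMP entered | Steroid entered | IMP value in SAP table | IMP value under stated rule | Agree? |
|---|---|---|---|---|---|
| 1 | missing | missing | related | related | yes |
| 2 | related | missing | related | related | yes |
| 3 | not related | missing | not related | not related | yes |
| 4 | missing | related | not related | related | **no** |
| 5 | missing | not related | related | related | yes |

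The table follows the rule in two of the three rows with a missing IMP causality (1 and 5) and breaks it in row 4.

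**Effect on event counts.** If k TEAEs fall in row 4, the IMP-related event count is short by exactly k. The documents do not give k, and zero is possible.

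**Effect on the rate.** SAP 11.2 states: "TEAE rates per time at risk will be calculated as annualized TEAE rates using" the number of events divided by (observation days / 365.25). The inputs are 63 subjects per sequence (Protocol 10.1) and, as an assumption, full Period 1 follow-up of 24 weeks × 7 = 168 days each.

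- Days: 63 × 168 = 10,584
- Patient-years: 10,584 / 365.25 = 28.98
- Change per event: 1 / 28.98 = 0.0345 per patient-year
- With 20% less follow-up (assumed): 0.8 × 28.98 = 23.18 patient-years, so 1 / 23.18 = 0.0431
- For an assumed range of k from 0 to 10 in one arm with full follow-up: 0 to 10 / 28.98 = 0.345 per patient-year

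**Effect on the percentage of subjects.** One subject moves one arm by at most 1 / 63 = 1.6 percentage points. In the SAF-IgPro20 set the figure is 1 / 126 = 0.8 points if all 126 subjects enter that set. Either shift occurs only if the subject has no other IMP-related TEAE.

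**What does not move.** The counts of all TEAEs, all serious TEAEs, all AESIs and steroid-related TEAEs do not use the imputed IMP value. The thromboembolic stopping formula in SAP 11.3 has no causality term. An event within 72 hours of an infusion also stays in the SAP 11.2 category that combines causal and temporal association.

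**The case against.** The best defence is that attribution was meant to be exclusive. No row of the table ends with both causes *related*, and row 4 mirrors row 2, where a missing steroid causality becomes *not related* because IMP is already *related*. The eCRF wording in Protocol 9.3 can be read as an either/or choice. On that reading a positive steroid entry settles the IMP field, an assessment has been provided, and the protocol's default for an absent assessment is not triggered. The doubt rule can likewise be read as an instruction to the investigator at entry, not as an imputation rule.

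This makes the conflict with the protocol arguable, and the charge that SAP Section 5 omits a departure is conditional on it. It does not rescue the SAP text. The SAP never states exclusivity. Its table treats the two causalities as separate fields, each of which can be missing on its own. Its declared principle is the worst case for IMP, which row 2 meets and row 4 does not. Even if exclusivity was intended, the lead-in sentence is wrong for row 4 and has to change.

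Two further points stand and limit the consequences. Protocol 9.6.3 requires a causality entry for every SAE, Protocol 9.6.2 puts AESIs under the same reporting procedure, and Protocol 13.5.2 provides for data queries, so surviving row 4 records among serious events and AESIs should be rare. Also, SAP Table 1 does not say which cause its related-TEAE measures refer to. If they cover either cause, row 4 events still count there, and the loss is confined to the IMP-specific summaries in SAP 11.2.

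**Conclusion.** The concern holds. Row 4 contradicts the sentence it is meant to carry out, and that conclusion needs no assumption about the eCRF. Protocol 9.3 points the same way, though less conclusively.

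The likely size is small and cannot be fixed from the documents, because the number of affected records is unknown. The per-event and per-subject figures above are conditional on at least one such record, on 63 subjects per arm, and on the follow-up assumed. Row 4 applies in both sequences, so the effect on the comparison of IgPro20 with placebo has no known direction. Efficacy results are untouched. This should be corrected, but it does not threaten the trial's main conclusions.

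**What to change.** In the SAP 8.1.1 table, set the imputed IMP value in row 4 to *related* and leave the corticosteroid value *related* as entered. Add a footnote saying that this is the only row with a dual attribution. Every missing IMP causality is then imputed the same way, in line with the lead-in sentence and Protocol 9.3. Report, by sequence and period, the number of adverse events whose IMP causality was imputed, so that readers can see how much rests on the rule. Make the change before unblinding for the EOP1 analysis, as SAP Section 3 requires for decisions on the primary data analysis.

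The cost is one table cell, one footnote, one line of code and one reported count. The IMP-related totals may be slightly higher, and a row 4 event will appear in both the IMP-related and the steroid-related summaries.
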